5.2.4 Electrocardiogram

5.2.4.1 12-lead resting ECG

Recording

Twelve-lead resting ECGs (I, II, III, aVR, aVL, aVF, V1 - V6) will be recorded using a computerised electrocardiograph (CardioSoft EKG System, GE Medical Systems, Freiburg, Germany) at the time points given in the [Flow Chart](#). Electrode placement will be performed according to the method of Wilson, Goldberger and Einthoven modified by Mason and Likar (hips and shoulders instead of ankles and wrists). Precise electrode placement will be marked with an indelible mark on the skin to allow reproducible placement throughout the inhouse confinement.

To achieve a stable heart rate at rest and to assure high quality recordings, the site personnel will be instructed to assure a relaxed and quiet environment so that all subjects are at complete rest.

All ECGs will be recorded for 10 sec duration after subjects have rested for at least 5 min in a supine position. ECG recording should precede all other study procedures scheduled for the same time to avoid compromising ECG quality.

ECGs will be recorded as single ECGs or as triplicate ECGs (i.e. three single ECGs recorded within 180 sec) as indicated in the Flow Chart.

ECGs may be repeated for quality reasons for instance due to alternating current artefacts, muscle movements, or electrode dislocation. For repetition within triplicate ECGs the time window of 180 sec applies as well. The repeat ECGs are assigned to the respective scheduled time point.

Additional (unscheduled) ECGs may be recorded for safety reasons. These ECGs are assigned to the prior scheduled time point in the sponsor's database.

Storing

All ECGs will be stored electronically on the Muse Cardiology Information System (GE Medical Systems, Freiburg, Germany).

Data transfer

For time points specified in the Flow Chart, ECGs will be transferred electronically to the central ECG lab for evaluation.

All ECG recordings including repeat ECGs will be sent to the central ECG lab which will select the ECGs with the best quality at each time point.

Proprietary confidential information © 2018 Boehringer Ingelheim International GmbH or one or more of its affiliated companies

Unscheduled ECGs (for safety reasons) will be transferred to the central ECG lab but will not be included into the statistical analysis of interval lengths.

Data transfer from the central ECG lab to the sponsor is described in the ECG data transfer agreement (see TMF).

Proprietary confidential information © 2018 Boehringer Ingelheim International GmbH or one or more of its affiliated companies

Abnormal findings, irrespective of whether they originate from central or local evaluation, will be reported as AEs (during the trial) or baseline conditions (at screening) if judged clinically relevant by the investigator.

Any ECG abnormalities will be monitored carefully and, if necessary, the subject will be removed from the trial and will receive the appropriate medical treatment.

5.2.4.2 Continuous ECG monitoring

Cardiac rhythm (including heart rate) will be monitored by means of continuous 3-lead ECG recording using the CARESCAPE Monitor B450 (GE Healthcare, Freiburg, Germany) for at least 15 min before drug administration (for baseline assessment) and for 4 h following drug administration. This continuous ECG monitoring supports the early detection of adverse events such as clinically relevant bradycardia, tachycardia, or arrhythmia at the trial site. Beyond this clinical evaluation at the trial site, no further data collection or analyses are performed based on continuous ECG monitoring.

ECG data from continuous ECG recording will not be transferred to the clinical trial database. Abnormal findings during continuous ECG recording will be recorded as AEs if judged clinically relevant by the Investigator.

5.2.5 Assessment of other safety parameters

5.2.5.1 Vital signs

Systolic and diastolic blood pressures (BP) as well as pulse rate (PR) or heart rate (heart rate is considered to be equal to pulse rate) will be measured by a blood pressure monitor (Dinamap Pro 100, GE Medical Systems, Freiburg, Germany) at the times indicated in the [Flow Chart](#), after subjects have rested for at least 5 min in a supine position. All recordings should be made using the same type of blood pressure recording instrument on the same arm if possible.

5.2.5.2 Medical examinations

At screening, the medical examination will include demographics including height and body weight, smoking and alcohol history, relevant medical history and concomitant therapy, review of inclusion and exclusion criteria, review of vital signs (BP, PR), 12-lead ECG (including rhythm strip of at least 15 minutes), laboratory tests, and a physical examination. At the end of trial examination, it will include review of vital signs, 12-lead ECG, laboratory tests, and a physical examination.

5.4 APPROPRIATENESS OF MEASUREMENTS

All measurements performed during this trial are standard measurements and will be performed in order to monitor subjects' safety and to determine pharmacokinetic and pharmacodynamic parameters in an appropriate way. The scheduled measurements will allow monitoring of changes in vital signs, standard laboratory values, and ECG parameters that might occur as a result of administration of trial medication. The safety assessments are standard, are accepted for evaluation of safety and tolerability of an orally administered drug, and are widely used in clinical trials. The pharmacokinetic parameters and measurements outlined in [Section 5.5](#) are generally used assessments of drug exposure. The biomarkers and measurements outlined in [Section 5.6](#) are of exploratory nature only.

5.5 DRUG CONCENTRATION MEASUREMENTS AND PHARMACOKINETICS

Date and clock time of drug administration and pharmacokinetic sampling will be recorded. Exact time points of plasma sampling will be derived from the study management system ClinBase™ and documented in the CRFs by the medical personnel or sent as electronic files to the trial data manager. The actual sampling times will be used for determination of pharmacokinetic parameters.

PK sampling times and periods may be adapted during the trial based on information obtained during trial conduct (e.g., preliminary PK data) including addition of samples and visits as long as the total blood volume taken per subject does not exceed 500 mL. Such changes would be implemented via non-substantial CTP Amendments.

5.5.1 Pharmacokinetic endpoints

The following pharmacokinetic parameters will be determined if feasible:

5.5.1.1 Secondary endpoints

- $AUC_{0-\infty}$ (area under the concentration-time curve of the analyte in plasma over the time interval from 0 extrapolated to infinity)
- C_{\max} (maximum measured concentration of the analyte in plasma)

5.5.2 Methods of sample collection

5.5.2.1 Plasma sampling for pharmacokinetic analysis

For quantification of BI 1323495 plasma concentrations, 2.7 mL of blood will be taken from an antecubital or forearm vein into an K₂-EDTA (dipotassium ethylenediaminetetraacetic acid)-anticoagulant blood drawing tube at the times indicated in the [Flow Chart](#). Blood will be withdrawn by means of either an indwelling venous catheter or by venipuncture with a metal needle.

After completion of the trial, the plasma samples may be used for further methodological investigations, e.g. for stability testing, assessment of metabolites. However, only data related to the analyte and/or its metabolite(s) including anti-drug antibodies (if applicable) will be generated by these additional investigations. The study samples will be discarded after completion of the additional investigations but not later than 5 years upon the final study report has been signed.

5.5.3 Analytical determinations

BI 1323495 concentrations in plasma will be determined by validated LC-MS/MS (liquid chromatography tandem mass spectrometry) assays. All details of the analytical methods will be available prior to the start of sample analysis. The analyses will be performed at

As described in [Section 4.1.5](#), the bioanalyst will be unblinded during sample analysis.

5.7 PHARMACOKINETIC - PHARMACODYNAMIC RELATIONSHIP

The relationship of BI 1323495 plasma concentrations and biomarker results will be investigated in an exploratory manner
Other correlations will be explored as applicable.

6. INVESTIGATIONAL PLAN

6.1 VISIT SCHEDULE

Exact times of measurements outside the permitted time windows will be documented. The acceptable time windows for screening and end of trial examination are given in the [Flow Chart](#).

Study measurements and assessments scheduled to occur ‘before’ trial medication administration on Day 1 are to be performed and completed within a 3 h-period prior to the trial drug administration (including blank values for PK and biomarkers).

The acceptable deviation from the scheduled time for vital signs, ECG and laboratory tests will be \pm 15 min for the first 4 h after trial drug administration and \pm 30 min thereafter.

Starting from 48 h post administration a deviation from the scheduled time for vital signs, ECG and laboratory tests (including PK) of \pm 120 min is acceptable.

If several activities are scheduled at the same time point in the [Flow Chart](#), ECG should be the first and meal the last activity. Furthermore, if several measurements including venipuncture are scheduled for the same time, venipuncture should be the last of the measurements due to its inconvenience to the subject and possible influence on physiological parameters.

For planned individual plasma concentration sampling times refer to the [Flow Chart](#). While these nominal times should be adhered to as closely as possible, the actual sampling times will be recorded and used for determination of pharmacokinetic parameter.

If a subject misses an appointment, it will be rescheduled if possible. The relevance of measurements outside the permitted time windows will be assessed no later than at the Report Planning Meeting.

6.2 DETAILS OF TRIAL PROCEDURES AT SELECTED VISITS

6.2.1 Screening period

After having been informed about the trial, all subjects will give their written informed consent in accordance with GCP and local legislation prior to enrolment in the study.

For information regarding laboratory tests (including drug and virus screening), ECG, vital signs, and physical examination, refer to [Sections 5.2.3 to 5.2.5](#).

Pharmacogenomic genotyping will be performed in those volunteers whose genotypes are not known (for details see [Section 5.3](#)).

6.2.2 Treatment period

Each subject will receive one dose of the respective trial medication (BI 1323495 or placebo) at Visit 2.

Proprietary confidential information © 2018 Boehringer Ingelheim International GmbH or one or more of its affiliated companies

Trial medication will be taken orally by each subject under direct supervision of the investigator or designee. Details on treatments and procedures of administration are described in [Section 4.1.4](#).

Study participants will be admitted to the trial site in the morning of Day 1 and kept under close medical surveillance for at least 34 h following drug administration. The subjects will then be allowed to leave the trial site after formal assessment and confirmation of their fitness by the investigator or designee. From Day 3 onwards, the study will be performed in an ambulatory fashion.

For details on time points and procedures for collection of blood samples for PK analysis, refer to [Flow Chart](#) and [Section 5.5.2](#).

For details on time points and procedures for collection of blood samples for PD analysis, refer to [Flow Chart](#) and [Section 5.6.2](#).

The safety measurements performed during the treatment period are specified in [Section 5.2](#) of this protocol and in the Flow Chart. For details on time points for all other trial procedures, refer to the Flow Chart. AEs and concomitant therapy will be assessed continuously from screening until the end of trial examination.

6.2.3 End of trial period

For AE assessment, laboratory tests, recording of ECG and vital signs, and physical examination during the end of trial period, see [Sections 5.2.2](#) to [5.2.5](#).

Subjects who withdraw before the end of the planned treatment period should undergo the end of trial visit.

All abnormal values (including laboratory parameters) that are judged clinically relevant by the investigator will be monitored using the appropriate tests until a return to a medically acceptable level is achieved. (S)AEs persisting after subject's end of trial must be followed up until they have resolved, have been sufficiently characterised, or no further information can be obtained.

The end of the trial as a whole is defined by the 'last regular visit completed by last subject' or 'end date of the last open AE' or 'date of the last follow-up test' or 'date of an AE has been decided as sufficiently followed-up', whichever is latest.

7. STATISTICAL METHODS AND DETERMINATION OF SAMPLE SIZE

7.1 STATISTICAL DESIGN – MODEL

7.1.1 Objectives

The primary objective of this trial is to investigate the safety and tolerability of BI 1323495 by using descriptive statistics for all endpoints comparing active dose groups to placebo.

The secondary objective is the exploration of the pharmacokinetics (PK) and pharmacodynamics (PD) of BI 1323495.

7.1.2 Endpoints

Safety and tolerability will be determined on the basis of the primary endpoint and the additional criteria specified in [Section 5.2.1](#). PK and PD endpoints are specified in [Sections 5.5.1](#) and [5.6.1](#), respectively.

7.1.3 Model

Endpoints will be analysed by descriptive statistics. Inferential statistics is not planned (as explained in [Section 7.2](#)).

Secondary endpoints, as defined in [Section 5.5.1.1](#), will be subjected to analysis of dose proportionality by use of the power model.

7.2 NULL AND ALTERNATIVE HYPOTHESES

Safety and tolerability of the different dose groups of BI 1323495 are to be determined on the basis of the investigated parameters in comparison to placebo. It is not planned to test any statistical hypotheses with regard to these variables in a confirmatory sense. Instead, they will be described in their entirety and evaluated by descriptive statistical methods.

Confidence intervals will be computed and will have to be interpreted in the perspective of the exploratory character of the study, i.e. confidence intervals are considered as interval estimates for effects.

7.3 PLANNED ANALYSES

All individual data will be listed.

Adherence to the protocol (such as inclusion/exclusion criteria, times of measurement, compliance with intake of trial medication, treatment dispensing errors, prohibited concomitant medication, completeness, and consistency of data) will be checked. Important protocol violations (IPVs) will be identified no later than in the Report Planning Meeting and provided in the TSAP.

7.3.1 Primary analyses

Analysis of safety and tolerability is described in [Section 7.3.3](#).

7.3.2 Secondary analyses

The secondary parameters (refer to [Section 5.5.1](#)) will be calculated according to the BI Standard Operating Procedure (SOP) ‘Standards and processes for analyses performed within Clinical Pharmacokinetics/Pharmacodynamics’ ([001-MCS-36-472](#)). Analyses will be performed for parent drug.

Plasma concentration data and parameters of a subject will be included in the statistical PK analyses if they are not flagged for exclusion due to a protocol violation relevant to the evaluation of PK (to be decided no later than in the Report Planning Meeting) or due to PK non-evaluability (as revealed during data analysis, based on the criteria specified below). Exclusion of a subject’s data will be documented in the CTR.

Relevant protocol violations may be:

- Incorrect trial medication taken, i.e. the subject received at least one dose of trial medication the subject was not assigned to
- Incorrect dose of trial medication taken
- Use of restricted medications

Plasma concentrations and/or parameters of a subject will be considered as non-evaluable, if for example:

- The subject experienced emesis that occurred at or before two times median t_{max} of the respective treatment (median t_{max} is to be determined excluding the subjects experiencing emesis),
- Missing samples/concentration data at important phases of PK disposition curve.

The PK parameter analysis set (PKS) includes all subjects in the Treated Set (TS) who provide at least one PK parameter that was not excluded according to the description above.

α β

Based on the estimate for slope parameter (β), a 2-sided 95% CI for the slope will be computed. Perfect dose proportionality would correspond to a slope of 1. The assumption of a linear relationship between the log-transformed pharmacokinetic endpoint and the log-transformed dose will be checked.

If dose proportionality over the entire dose range investigated cannot be shown, an attempt will be made to identify dose range(s), where dose proportionality can be assumed.

To support the analyses of dose proportionality, graphical representations of the data might be created. These might include (but are not limited to) individual time-courses of plasma concentrations and the (geometric) mean plasma concentration time profiles.

7.3.3 Safety analyses

Safety will be assessed for the endpoints and parameters of interest listed in [Section 5.2.1](#). All treated subjects (that is, all subjects who received at least one dose of study drug), will be included in the safety analysis. For additional analyses sets used in the ECG evaluation see TSAP for further details. Safety analyses will be descriptive in nature and will be based on BI standards. No hypothesis testing is planned.

Treatments will be compared in a descriptive way. The placebo control group in the safety evaluation will consist of all placebo treated subjects, regardless of the dose group in which they were treated. The active treatment groups will be compared to the placebo group in a descriptive way. Tabulations of frequencies/proportions will be used for the evaluation of categorical (qualitative) data, and tabulations of descriptive statistics will be used to analyse continuous (quantitative) data.

The analyses will be done by ‘treatment at onset’.

The REP for BI 1323495, the time interval when measurable drug levels or PD effects are still likely to be present after administration, is not known for this first-in-human trial. Therefore, all AEs with an onset between start of treatment and the end of trial examination (last per protocol contact) will be considered on treatment.

Measurements (such as ECG, vital signs, or laboratory parameters) or AEs will be assigned to treatments (see [Section 4.1](#)) based on the actual treatment at the planned time of the measurement or on the recorded time of AE onset (concept of treatment emergent AEs).

Therefore, measurements planned or AEs recorded prior to intake of trial medication will be assigned to 'screening' and those between trial medication intake until the end of trial visit will be assigned to the treatment period. These assignments including the corresponding time intervals will be defined in detail in the TSAP. Please note that AEs occurring after the last per protocol contact but entered before database lock will be reported to drug safety only and will not be captured in the trial database.

Additionally, further treatment intervals (analysing treatments) may be defined in order to provide summary statistics for time intervals, such as combined treatments, on-treatment totals or periods without treatment effects (such as screening and post-study intervals).

Adverse events will be coded using the Medical Dictionary for Regulatory Activities (MedDRA). Frequency, severity, and causal relationship of AEs will be tabulated by treatment, system organ class, and preferred term. SAEs, AESIs (see [Section 5.2.2.1](#)), and other significant AEs (according to ICH E3) will be listed separately.

Laboratory data will be compared to their reference ranges. Values outside the reference range as well as values defined as clinically relevant will be highlighted in the listings. Additionally, differences from baseline will be evaluated.

Vital signs or other safety-relevant data observed at screening, baseline, during the course of the trial and at the end-of-trial evaluation will be assessed with regard to possible changes compared to findings before start of treatment.

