5.2 SAFETY

5.2.1 Endpoints of safety

Primary endpoint to assess safety and tolerability of BI 1323495 is the number [N (%)] of subjects with drug-related adverse events.

Further criteria of interest:

- AEs (including clinically relevant findings from the physical examination)
- Safety laboratory tests
- 12-lead ECG
- Continuous ECG monitoring
- Vital signs (blood pressure, pulse rate)

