5.2.2.2 Adverse event collection and reporting

AE collection

Upon enrolment into a trial, the subject's baseline condition is assessed (for instance, by documentation of medical history/concomitant diagnoses), and relevant changes from baseline are noted subsequently.

Subjects will be required to report spontaneously any AEs as well as the time of onset, end, and intensity of these events. In addition, each subject will be regularly assessed by the medical staff throughout the clinical trial and whenever the investigator deems necessary. As a minimum, subjects will be questioned for AEs (and concomitant therapies) at the time points indicated in the [Flow Chart](#). Assessment will be made using non-specific questions such as 'How do you feel?'. Specific questions will be asked wherever necessary in order to more precisely describe an AE.

A carefully written record of all AEs shall be kept by the investigator in charge of the trial. Records of AEs shall include data on the time of onset, end time, intensity of the event, and any treatment or action required for the event and its outcome.

The following must be collected and documented on the appropriate CRF(s) by the investigator:

- From signing the informed consent onwards until an individual subject's end of trial:
 - All AEs (serious and non-serious) and all AESIs
 - The only exception to this rule are AEs (serious and non-serious) and AESIs in Phase I trials in healthy volunteers, when subjects discontinue from the trial due to screening failures prior to administration of any trial medication. In these cases, the subjects' data must be collected at trial site but will not be entered in the CRF or trial database and will not be reported in the CTR.
- After the individual subject's end of trial:
 - The investigator does not need to actively monitor the subject for new AEs but should only report any occurrence of cancer and related SAEs and related AESIs of which the investigator may become aware by any means of communication, e.g. phone call. Those AEs should, however, not be reported in the CRF.

AE reporting to sponsor and timelines

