## 6. GENERAL ANALYSIS DEFINITIONS

### 6.1 TREATMENTS

It is planned that in total 64 healthy male subjects will participate in this study, according to 8 sequential groups comprising 8 subjects per group. Within each dose group, 6 subjects will receive the active drug and 2 will receive placebo.

For details of dosage and formulation see Table 6.1:1 below.

Table 6.1: 1 Labels for treatments for use in the CTR

Dose group	Treatment			Short label
1-8	P*	Placebo, tablet, qd		Placebo
1	A	BI 1323495, tablet, po, qd		BI
2	B	BI 1323495, tablet, po, qd		BI
3	C	BI 1323495, tablet, po, qd		BI
4	D	BI 1323495, tablet, po, qd		BI
5	E	BI 1323495, tablet, po, qd		BI
6	F	BI 1323495, tablet, po, qd		BI
7	G	BI 1323495, tablet, po, qd		BI
8	H	BI 1323495, tablet, po, qd		BI

\*: The placebo group in the safety evaluation will consist of all placebo treated subjects, regardless of the dose group in which they were treated.

The following separate study phases will be defined for the analyses of AEs:

- **Screening** (ranging from 0:00h (midnight) on day of informed consent until administration time of study drug (BI or Placebo))
- **On treatment**
  - **BI/Placebo treatment** (separately for each treatment, ranging from the time of administration of BI / Placebo until 0:00h (midnight) on the day after trial completion date)

Please note that all AEs reported between start of trial drug administration and the last per-protocol contact will be considered on treatment (i.e. no follow-up period is considered in this trial).

Two types of AE displays will be provided in the report:

**A)** Section 15.3 and Appendix 16.1.13.1.8 (for ClinicalTrials.gov and EudraCT) of the CTR displays:

In these displays, the on-treatment phase will be analysed (labelled with the name of the study treatment (short label)). Screening will not be included in this analysis.

The following totals will be provided in addition:

- a total over all BI treated phases ("BI Total")
- a total over all on treatment phases included in this analysis ("Total on treatment") (Section 15.3 only)

**B)** Section 15.4 and Appendix 16.1.13.1.8 (except for ClinicalTrials.gov and EudraCT) of the CTR displays:

- Screening
- On treatment (labelled with the name of the study treatment (short label))

In Section 16.1.13.1.8 AE tables, the following totals will be provided in addition:

- a total over all BI treated phases ("BI Total")
- a total over all study phases ("Total")

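### Cancers and drug-related SAEs and AESIs with onset after the last visit, even if known before lock, have no place in any planned AE table or listing

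*Protocol*

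**What the plan says.** Protocol 5.2.1 defines the primary endpoint as "the number [N (%)] of subjects with drug-related adverse events", with no time limit in the definition.

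Protocol 5.2.2.2 covers what happens once a subject has finished. The investigator need not look actively for new events, but "should only report any occurrence of cancer and related SAEs and related AESIs of which the investigator may become aware". It then adds: "Those AEs should, however, not be reported in the CRF".

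Protocol 7.3.3 treats AEs that start between dosing and the end-of-trial examination as on treatment, because the residual effect period is unknown in a first-in-human trial. For anything later it says that "AEs occurring after the last per protocol contact but entered before database lock will be reported to drug safety only", and it rules out capture in the trial database.

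SAP 6.1 follows this. It defines a screening phase and an on-treatment phase, notes that "no follow-up period is considered in this trial", and builds both types of AE display from those phases. SAP 7.8.1 plans separate tables for drug-related, serious, drug-related serious and special-interest events, plus EudraCT entries. Protocol 7.3.3 plans separate listings of SAEs and AESIs.

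**The concern.** After the last visit, the protocol picks out the late events that matter most for a new compound and asks for them to be reported. It then sends them down a channel that does not feed the analysis. Because this applies even to events already known when the database is locked, the loss does not come from late information. It is a stated rule.

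The reasoning behind the window also points two ways. An unknown residual effect period is a good reason to count every AE up to the last visit. It is equally a reason not to assume that drug effects have ended by then.

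At stake is how complete the safety tables and listings are in the first human data on this compound. A reader of those outputs could not tell whether there were no late related serious events or whether some were known and held elsewhere.

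**Working it through.** The plan gives no figure to reproduce, so the check is mainly a tracing exercise.

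**1. Which events are affected.** New onsets after the last per-protocol contact that are cancers, related SAEs or related AESIs (Protocol 5.2.2.2). AEs that start before the last visit are captured and followed beyond it (Protocol 5.2.2.2 and 6.2.3), so they are not affected.

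**2. Where an affected event goes.**

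| Destination | Included? | Source |
|---|---|---|
| Sponsor's drug safety function | Yes | Protocol 5.2.2.2, 7.3.3 |
| CRF | No | Protocol 5.2.2.2 |
| Trial database | No | Protocol 7.3.3 |
| SAP screening phase | No, this ends at dosing | SAP 6.1 |
| SAP on-treatment phase | No, this ends with the trial completion date | SAP 6.1 |
| SAP follow-up phase | Does not exist | SAP 6.1 |
| Report text | Neither required nor forbidden in the readable text | Both documents |

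**3. What follows for the outputs.** SAP Section 3 stores study data in the trial database. An event outside the database and outside both phases cannot enter the primary-endpoint count, the SAE or AESI tables and listings, or the registry displays. The registry displays use the on-treatment phase only (SAP 6.1).

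**4. How much time there is for such an event to become known before lock.** First doses in successive groups are at least 6 days apart, and there are 8 groups (Protocol 3.1). The minimum gap between first dosing in group 1 and in group 8 is (8 − 1) × 6 = 42 days. Assume that all eight groups are dosed and that the end-of-trial visit falls equally long after dosing in each group. The Flow Chart is not in the public text, so this cannot be confirmed. Then the first group 1 subject finishes at least 42 days before the first group 8 subject, and lock comes later still.

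**5. Illustration of size.** Each group has 6 active subjects, so 8 × 6 = 48 in total. Assume exactly one late drug-related SAE, in an active subject, with no other drug-related AE among the subjects counted. Exact (Clopper-Pearson) 95% intervals:

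| Count | Without the late event | With it |
|---|---|---|
| Dose group | 0/6 = 0% (0 to 45.9%) | 1/6 = 16.7% (0.4 to 64.1%) |
| All active | 0/48 = 0% (0 to 7.4%) | 1/48 = 2.1% (0.05 to 11.1%) |

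The endpoint counts subjects. If the same subject already had a drug-related AE on treatment, the primary count would not change at all. The table shows what one event could do. It says nothing about how likely one is.

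**The case against.** The case on the other side is substantial, and most of it stands.

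- **The rule is clear and consistent.** Protocol 5.2.2.2, Protocol 7.3.3 and SAP 6.1 agree, so there is no contradiction to resolve. Counting every AE up to the last visit is the inclusive choice within active follow-up.
- **The primary count is best left alone.** A reader might infer that late events should be added to it. After the last visit, ascertainment is passive and limited mainly to events judged related, and the investigator knows the treatment (Protocol 4.1.5.2). Mixing those reports with actively collected AEs would blur the comparison with placebo.
- **Subject protection is intact.** A reader might infer that late serious events escape oversight. They do not. SAEs and AESIs go to the sponsor within 24 hours (Protocol 5.2.2.2), and the rule on drug-related SAEs in Protocol 3.3.4.2 acts on reported events, whether or not they are in the database.
- **The report is not bound to be silent.** A reader might infer that the clinical trial report must show no such event. The documents do not say so. For screening failures, Protocol 5.2.2.2 expressly excludes the data from the report. For late events it excludes them only from the CRF. The corporate AE guideline cited in SAP 7.8.1 is not available here and may provide for narratives.
- **The post-study intervals in Protocol 7.3.3 are not a ready-made home.** They are described as periods free of treatment effects, which does not suit events judged drug-related.
- **Likelihood cannot be judged.** The half-life is redacted and the end-of-trial day is not shown.

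None of this fills the remaining gap. The readable text of the two documents does not require known late related events to be listed, described or reconciled anywhere in the report.

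**Conclusion.** The point holds as a reporting gap. Under the written rules, a cancer, drug-related SAE or drug-related AESI with onset after the last per-protocol contact appears in no planned AE table or listing, even if the sponsor knows of it before lock. This follows from the text and needs no numerical assumption beyond the database being the source of the tables.

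Its size cannot be estimated. Few such events are to be expected after a single dose, and there may be none. The 0/6 versus 1/6 contrast is illustrative and depends on there being no other drug-related AE in that group. The gap still deserves correction, because none and one late related serious event are materially different findings in a first-in-human report, and the correction is cheap.

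The documents do not support the stronger conclusions: that the primary endpoint is wrongly defined, that the events are lost to safety oversight, or that they are barred from the report.

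**What to change.** Keep the on-treatment window and the primary-endpoint count as they are.

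- **Protocol 7.3.3:** replace the drug-safety-only rule with a requirement that, before lock, all cancers, related SAEs and related AESIs known to drug safety with onset after the last per-protocol contact are reconciled and shown by treatment in a separate listing in the clinical trial report. The CRF rule in Protocol 5.2.2.2 can stand if the drug safety records are the source.
- **SAP 6.1 and 7.8.1:** define that listing, label it as post-trial and passively ascertained, and add a footnote to the primary-endpoint, SAE and AESI tables giving the number of such events, including when it is zero.

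The cost is some wording, one reconciliation, one listing and one footnote. The limitation is that these events cannot be compared between groups on the same footing as on-treatment events, and the label makes that plain.
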